## 5. Study outcomes

## 5.1. Outcome variables

Primary and secondary outcomes and process measures are displayed in Table 1.

Primary outcome: Our primary outcome is whether patients obtain a follow-up colonoscopy within 1 year of having an abnormal FIT result, as assessed through chart audit. Because the navigator's role involves tracking completed colonoscopies and communicating colonoscopy results to patients, it is likely that navigated patients will have more complete capture of colonoscopy events (our primary outcome) than usual care patients. To minimize bias in the collection of primary outcome data across study arms, the study team will implement an adjudication process, where systematic chart abstraction and medical records requests to referring gastroenterologists (GIs) will be performed by an abstractor who is blinded to study arm assignment (See Section 6 below). Starting after the 1-year evaluation interval, procedure and pathology reports from all study patients without electronic health record-evidence of a completed colonoscopy will be requested, and adjudicated by the project chart auditor; the GI and clinical champion will be consulted as questions arise.

Secondary outcomes include time to colonoscopy receipt and adequacy of bowel preparation (% adequate). We will also report colonoscopy outcomes (N, % adenomas and advanced adenomas detected; n cancers found). (See Handling of Deviations and Protocol Amendments 9.3)

## Table 1. Study Outcomes

| Variable   | Definition  | Numerator  | Denominator  |  |  |
|--|---|--|--|--|--|
| Primary outcomes   |   |  |  |  |  |
| Colonoscopy
completed   | A colonoscopy is
completed within 12
mo of the patient's
FIT positive test date                    | No. of patients with
completed colonoscopy within
12 mo of FIT positive test date  | No. of eligible patients
enrolled in study, with
exclusions for patients
randomized in error  |  |  |
| Cost and cost-
effectiveness (See
Handling of
Deviations and
Protocol
Amendments 7.x) | Cost per program
component, per-
patient cost, and cost
per additional
completed
colonoscopy | Difference in cost to deliver program  | Difference in program
effectiveness   |  |  |
| Secondary outcomes   |   |  |  |  |  |
| Time to colonoscopy  | Time from FIT
positive test result to
completed
colonoscopy  | Hazard of obtaining a colonoscopy by 365 days  | No. of eligible patients
enrolled in study, with
exclusions for patients
randomized in error  |  |  |
| Adequate bowel preparation quality   | Bowel preparation is
considered adequate
by the endoscopist
performing the
colonoscopy          | No. of patients with adequate
bowel preparation,
preparation is (excellent,
good, or fair) and no
alterations are made to
rescreening interval because
of bowel prep quality** | No. of patients with a
performed colonoscopy
during the study period
(include patients for whom
the procedure was
discontinued because of poor
bowel prep) |  |  |
| Colonoscopy
outcomes  | Adenomas, advanced
adenomas, or cancer
detected   | No. of patients with
adenomas, advanced
adenomas, or cancer detected
(based on pathology report)  | No. of patients with a performed colonoscopy during study period   |  |  |

#### 5.2. Covariates

We will treat county as a covariate in all analyses as it was a randomization stratification variable.

## 5.3. Potential moderators of effectiveness

The following variables will be tested as potential moderators of effectiveness:

| Potential Moderator                 | Categories   |
|-------------------------------------|--|
| Sex                                 | Male, female   |
| Preferred language                  | English, Spanish, Other                              |
| Age                                 | 50–54, 55–59, 60–64, 65–69, and 70–75                |
| Insurance status                    | Medicaid, Medicare, self-pay (uninsured), commercial |
| Probability of patient adherence to | Low: 0 < .52, Moderate: .52 < .63, High: ≥.63)       |
| navigation (based on risk score)    |  |

- sex (patient navigation will be more effective in women vs. men)
- preferred language (patient navigation will be more effective in patients who preferred Spanish vs. English; participants who indicated other will not be included in this analysis
- age (patient navigation was more effective in younger vs older age groups, defined as (50–54, 55–59, 60–64, 65–69, and 70–75)
- Insurance status (patient navigation will be more effective in uninsurance adults vs. insured adults)
- Probability of patient adherence to colonoscopy without navigation (patient navigation will be more effective in patients having lower probability of adherence, based on risk score)
- See Handling of Deviations and Protocol Amendments 9.6

#### 6. Statistical Methods

#### 6.1. Primary outcome analysis

Primary analysis will rely on a modified intention-to-treat (ITT) that excludes patients from both arms who are randomized in error (determined to be ineligible based on information in the medical record that was missed during the eligibility determination process). Patients in the primary ITT data analysis will retain their randomization assignment irrespective of whether they received patient navigation. Two secondary per-protocol analyses are planned: one that excludes patients who were determined ineligible because they moved, or clinical reasons that occurred post-randomization; and a second that additionally excludes patients who were never reached by the navigator.

Sea Mar's EHR data will be transferred to CHR every 6 months via a secure file transfer. We will examine the distribution of all variables prior to analyses and verify all missing and out-of-range values. We will assess the ICC. If the ICC is .001 or above, we will use hierarchical generalized linear modeling to account for clustering of patients within clinics. If the ICC is less than .001, we will use adjusted logistic regression without accounting for clustering to optimize parsimony. Because the primary outcome is binary (i.e., follow-up colonoscopy, yes/no), we will use a model with a logit link and binomial distribution (i.e., multilevel logistic regression). The independent variable will be arm (dummy-coded) with usual care as the reference group. 'Clinic' will be modeled as a random effect. The model will include county as a covariate (fixed effect) as it was a stratification factor for randomization.

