## 3. Randomization and blinding

Patients meeting clinical eligibility criteria will be randomized by the health center (Sea Mar) analyst to receive either the patient navigation intervention or usual care. Study identification numbers linked to patients will be uploaded into REDCap® on a weekly basis, for patients in the navigation arm, with date of abnormal FIT result. We anticipate that the time between patient identification and study randomization will take about 2 weeks. (See **Handling of Deviations and Protocol Amendments 9.4**)

Randomization will be performed using a stratified approach that considers patients' county of residence. We will use Sealed Envelope (London, UK) to randomize patients 1:1 to navigation or usual care in blocks of 4 to 8 individuals, stratified on county of residence. For practical reasons, neither the research team nor the clinic staff will be blinded to randomization assignment. However, measures have been taken to preserve as much blinding as possible. Staff trained in navigation will not perform colonoscopy referral coordination (as part of usual care). Patients randomized to patient navigation are removed from the referral coordinator list to eliminate potential outreach by referral coordinators. In this way, the patient navigation intervention will not be overlaid on usual care, as doing so would result in multiple contacts from multiple clinic staff. (Consistent with usual care, referral

coordinators will contact referred patients who have not completed a colonoscopy making up to three phone attempts; patients who are not reached will be sent a letter.)

The randomization will result in 600 patients assigned to the patient navigation arm and 600 assigned to the usual care arm. We will assess rates of colonoscopy receipt at 1 year overall, and will perform a heterogeneity of treatment effect analysis to assess differential effects by age, sex, ethnicity, language preference, insurance status, and probability of adherence (based on the risk model), using data from the electronic health record.

CHR analysts will assign a colonoscopy completion probability, based on the risk prediction model. These methods have been described previously.

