#### 4. Sample size and power

Estimates of the ICC at the clinic level for CRC screening collected from several different studies range from .001 to .10, with the majority ranging from .02 to .05. The ICC for our prior CRC screening study in similar clinics (STOP CRC) was .03. Though we anticipate a lower ICC for this study given that we will partner with a single large federally qualified health center (FQHC) with more uniform procedures and practices (i.e., less betweenclinic variability) rather than eight smaller FQHCs in the STOP CRC trial, we will use an ICC estimate of .03 as a conservative upper estimate. Given that larger ICCs increase the design effect and reduce the power of the test, we will provide the minimum detectable odds ratios for the primary outcome for both a near zero ICC and an ICC of .03; we will base our analyses on an average cluster size of 42 patients per clinic (1200 abnormal FIT patients/32 clinics). Based on data from prior studies, we expect that 9% of patients will have a positive FIT, and 44% of patients under usual care will complete a follow-up colonoscopy within 1 year (based on chart abstracted data from 08/05/2017 to 08/04/2018 (N = 715 charts)). In a logistic regression framework, we will have 80% power to detect a difference of 12.9% (completion rate in intervention of 56.9%, OR=1.68) when accounting for the design effect and a difference of 9.2% (completion rate in intervention of 53.2%, OR=1.45), assuming no design effect at a two-tailed alpha level of .05. We believe a difference between 9.2% and 12.9% is both achievable and clinically significant. Notably, our minimal detectable difference is 2-3 times lower that the effect size reported in the New Hampshire Colorectal Cancer Screening Program (27 percentage points).

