## 6.3. Analysis of possible moderators

Our preliminary data showed follow-up colonoscopy receipt varied substantially by probability strata (30%, 59%, and 93% for the low, moderate, and high strata, respectively), suggesting that assessments of clinically meaningful impacts could differ by probability strata. To determine whether adherence probability moderates the effect of the intervention, we will add probability strata (moderate, low vs. high) and the product of stratum and arm to the primary outcome model. The product represents the interaction of arm and probability stratum; a significant term provides evidence for effect modification. We will determine the nature of any interaction by examining the simple main effects using graphical methods. We will repeat this analysis using the continuous risk score in place of the risk strata. We will have 80% power to detect an odds ratio for the product term, which represents the multiplicative change from the odds ratio for the moderate probability stratum for arm compared to the low probability stratum for arm of 2.98 (or 0.34 in the opposite direction), accounting for the design effect, and 2.17 (or 0.46 in the opposite direction) assuming no design effect, at a two-tailed alpha level of .05. Previous literature has reported significant differences in the effectiveness of patient navigation for colorectal cancer screening across patient subgroups defined by:

- Sex (patient navigation will be more effective in women vs. men)
- Preferred language (patient navigation will be more effective in patients who preferred Spanish vs. English; participants who indicated other will not be included in this analysis
- Age (patient navigation was more effective in younger vs older age groups, defined as (50–54, 55–59, 60–64, 65–69, and 70–75)
- Hispanic ethnicity (patient navigation will be more effective in Hispanic patients vs. non-Hispanic patients)
- Insurance status (patient navigation will be more effective in uninsurance adults vs. insured adults)
- Probability of patient adherence to colonoscopy without navigation (patient navigation will be more effective in patients having lower probability of adherence, based on risk score)
- See Handling of Deviations and Protocol Amendments 9.6

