# 7. Data auditing and validation

# Fidelity assessment and intervention dose (scientific rigor).

Our fidelity assessment will be designed in accordance with established methods outlined by the NIH Behavior Change Treatment Fidelity Workgroup and will focus on: (1) the accuracy of data capture for our primary and secondary outcomes (measurement fidelity), and (2) rigor and consistency with which the intervention is delivered (intervention fidelity). As part of intervention fidelity, we will assess the intervention dose. Intervention fidelity: To address intervention fidelity, research staff will monitor navigator calls with patients and provide feedback. A quality assurance tracker will be used by research staff to track content and timing of calls and identify areas for improvement. Any issues will be addressed during debrief meetings and booster training sessions.

- During the pilot, research staff will listen to a portion of patient calls for navigator coaching purposes.
- During the main trial, research staff will listen to 10 live calls every 3 months for the first year, and then 10 live calls every 6 months during the second year.

Qualitative patient interviews at the end of the program (n = 60) will gather patient-reported information on receipt of each call type, consistent with the NHCRCSP.

Intervention dose. As part of the fidelity assessment, we will track consistency of intervention dose: the number and content of phone calls delivered by patient navigators based on data collected from the patient navigation tracking system designed in REDCap®. The standard protocol includes six timed phone calls that address predefined content areas; thus, dose will be calculated as the proportion of phone calls completed and/or content areas addressed (with 6 as the denominator).

| NAVIGATION PROTOCOL TOPIC AREAS                   | COMPLETE IF DELIVERED BY  |  |
|---|---|--|
| Topic 1 – Introductory Call                       | Within 1-7 days of navigator assignment                           |  |
| Topic 2 – Barrier Resolution Calls                | Flexible timing prior to procedure                                |  |
| Topic 3 – Bowel Prep Review Call                  | 5-7 days before colonoscopy                                       |  |
| Topic 4 – Day before Colonoscopy Check-In
Call | Afternoon or evening before colonoscopy (text message acceptable) |  |

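### The second per-protocol analysis drops unreached patients from the navigation arm only, so it compares a reachable subset with an unselected usual-care arm

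*SAP*

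**What the plan says.** The primary analysis in SAP section 6.1 is a modified ITT. It removes patients randomized in error, explicitly from both arms, and otherwise follows assignment: "Patients in the primary ITT data analysis will retain their randomization assignment irrespective of whether they received patient navigation". Two secondary per-protocol analyses follow. The first removes patients who moved or became ineligible for clinical reasons after randomization. The other is "a second that additionally excludes patients who were never reached by the navigator". Section 6.2 repeats the rule, and neither section gives a counterpart for usual care.

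SAP section 3 keeps the two outreach streams apart. Navigation staff do not coordinate usual-care referrals, and "Patients randomized to patient navigation are removed from the referral coordinator list to eliminate potential outreach by referral coordinators". Usual-care patients receive up to three calls, and "patients who are not reached will be sent a letter".

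On adjustment, SAP section 5.2 says: "We will treat county as a covariate in all analyses as it was a randomization stratification variable". Section 6.1 adds a clinic random effect if the ICC is .001 or above. No weighting, matching or complier-type method is described.

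Reached is not defined. SAP section 7 measures dose out of six calls or topics, and accepts texts for the day-before and day-of contacts. Protocol section 5.e adds text outreach to patients who are hard to contact.

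**The concern.** Whether a patient is reached is observed after randomization, and here it is used to select one arm only. Read literally, every usual-care patient was never reached by a navigator, which would empty the comparator. The only workable reading is exclusion from the navigation arm alone. Usual care has its own hard-to-reach patients, and they remain. Keeping them is consistent with usual care, since the letter is part of it, but the two groups are then no longer comparable.

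A reader who sees a larger per-protocol figure beside the primary result may take it as the effect of navigation when it is actually delivered, although part of it may be selection. Because reached is undefined, the analysis set also depends on whether a text or voicemail is later counted as contact.

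**Working it through.** The SAP gives no figure for this analysis, so there is none to reproduce. The check asks how far the contrast moves under stated assumptions.

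**Inputs from the SAP**
- Usual-care completion at 1 year: 44% (section 4: "44% of patients under usual care will complete a follow-up colonoscopy within 1 year").
- Detectable difference without a design effect: 9.2 points, 53.2% against 44% (section 4), used as a yardstick.
- 600 patients per arm (section 3).

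**Assumptions**
- u is the share of navigation patients never reached, and q is the rate at which they would complete under usual care. The documents give neither.
- 30% for q borrows the preliminary low-stratum rate in section 6.3, as an anchor only.
- Exclusions from the first per-protocol set and clustering are ignored.

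**Bias when navigation has no effect**

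The rate among reached navigation patients is (0.44 − u·q)/(1 − u). Subtracting 0.44 gives

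bias = u·(0.44 − q)/(1 − u).

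At u = 20% and q = 30%: (0.44 − 0.06)/0.8 = 0.475, so the bias is +3.5 points. A simulation of 20,000 trials with 600 per arm gave +3.51. In percentage points:

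| u | q = 20% | q = 30% | q = 44% | q = 50% |
|---|---|---|---|---|
| 10% | +2.7 | +1.6 | 0 | −0.7 |
| 20% | +6.0 | +3.5 | 0 | −1.5 |
| 30% | +10.3 | +6.0 | 0 | −2.6 |

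The q = 30% column is 17%, 38% and 65% of 9.2 points. Against the SAP's other detectable difference, 12.9 points with the design effect, it is 12%, 27% and 47%.

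**Chance of a false finding for navigation**

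This is Φ(bias/SE − 1.96), with 600 usual-care and 600(1 − u) navigation patients. At u = 20% and q = 30%, SE = √(0.44·0.56/600 + 0.475·0.525/480) = 0.0305, and Φ(0.035/0.0305 − 1.96) = 20.8%. At u = 10% and 30% it is 7.6% and 47.2%. The nominal value is 2.5%.

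**When navigation works**

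Take a true modified-ITT effect of 9.2 points, u = 20%, and never-reached navigation patients completing at 30%.
- Reached navigation patients: (0.532 − 0.2·0.30)/0.8 = 0.590. The planned contrast is 0.590 − 0.44 = 15.0 points.
- If never-reached patients do equally well in either arm, reachable usual-care patients complete at (0.44 − 0.2·0.30)/0.8 = 0.475. The effect among the reachable is 11.5 points.
- If they would do 5 points better under usual care, that rate is (0.44 − 0.2·0.35)/0.8 = 0.4625. The effect is 12.75 points.

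The planned contrast overstates the effect by 3.5 or 2.25 points.

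**What a reader could recover**

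The two per-protocol sets are nested. If navigation counts were, for example, 264/600 in the first and 228/480 in the second, the never-reached group would be 36/120 = 30%. The SAP does not say that counts for both sets will be reported.

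**The case against.** The analysis is labelled secondary and per-protocol, carries no success criterion, and leaves the primary result alone. Conditioning on receipt is a known limit of such sets. This bears on severity and places the point at the low end of what should be changed, but the label does not make the arms comparable.

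The size rests on assumed values. SAP section 8.1 reports that the preliminary strata did not hold at the top (65% against an estimated 93%), section 5.3 uses different cut-points, and nothing ties unreached patients to the low stratum. The direction is also open. The outcome clock starts at the FIT, and randomization comes about two weeks after identification, so a patient who completes before contact could count as never reached with a favourable outcome. This stands, so the figures are illustrations. The one-sided selection does not depend on them.

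No completed contact in REDCap is a natural reading of never reached. That is fair for calls, but voicemails and outreach texts remain unclear.

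Withdrawing a planned contrast could look like selective reporting, particularly as SAP section 8 describes some analyses in the past tense. Showing the reached-only rate with its denominator answers this, because nothing is hidden. Adjusting for the predicted completion probability, which the trial calculates anyway, would reduce measured imbalance but not unmeasured reachability.

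**Conclusion.** The concern holds. As written, the rule selects the navigation arm on a post-randomization trait and leaves usual care unselected, with no adjustment for that trait. The design point is certain, while the size and sign of the bias are not. If never-reached patients would complete less often than average, the bias favours navigation: 1.6 to 6.0 points for 10% to 30% never reached at a 30% rate, and 2.7 to 10.3 at a 20% rate. It should be corrected, at modest priority.

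**What to change.** Do not present the reached-only set as a treatment-effect estimate. Report completion among reached and never-reached navigation patients, with n/N for each and no test against usual care. Define reached from the REDCap call data, stating whether a text or voicemail counts. The cost is wording and one definition.

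Optionally, if an effect among reachable patients is wanted, pre-specify a complier-average effect: the county-adjusted modified-ITT risk difference divided by the proportion reached in the navigation arm, with a bootstrap or delta-method interval. Three statements should go with it:
- Its population is the modified-ITT set, not the planned per-protocol set, which also drops patients who moved or became ineligible.
- It assumes that assignment to navigation has no effect in never-reached patients. This is strained, because they also leave the coordinator list.
- A sensitivity analysis lets never-reached patients do d better under usual care, giving (ITT + u·d)/(1 − u). The correction, u·d/(1 − u), runs from 0.1·3/0.9 = 0.3 to 0.3·5/0.7 = 2.1 points for u of 10–30% and d of 3–5 points, and moves toward navigation.

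The option costs a few lines of code, an extra assumption and a wider interval: about ±7.0 points at 20% never reached (roughly 5.6/0.8), against ±5.6 for the modified ITT, ignoring clustering. If the planned analysis has already been run, the definition and descriptive report still apply, and any complier-average estimate should be labelled post hoc.

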#### 8. Handling of Deviations and Protocol Amendments

- 8.1. Included all patients ages 50-75 with an abnormal FIT result, eliminated requirement of having moderate or high risk of follow-up colonoscopy non-adherence. Given the relatively low colonoscopy completion probability in the highest quintile group (65% vs. 93% estimated), we plan to randomize all eligible abnormal FIT patients. We will still prospectively calculate the patients' estimated probability of obtaining a colonoscopy, using the risk prediction model and preform subgroup analysis considering risk level as a moderator of effectiveness.
- 8.2. Eliminated cost and cost-effectiveness analysis. These analyses were eliminated because of COVID-19 resources constraints; through an official request to NCI dated 3/1/2021.
- 8.3. Eliminated no show/canceled appointments as a secondary outcome. We eliminated as an outcome noshow/canceled appointments because the number of referring GI practices would lead to inconsistencies and inaccuracies in the collection of these data.
- 8.4. Changed the randomization process. Following an electronic health record conversion, the original automated randomization in place at the partnering health center was disabled. As a result, from August 2021 through April 2022, patients were randomized weekly using the SURVEYSELECT procedure in SAS (Cary, NC).
- 8.5. Used Restricted Mean Survival Time for time-to-event analysis. To assess differences in time to colonoscopy completion between study arms (secondary outcome), we originally planned to use Cox proportional hazards and median survival time. Instead, we computed the log-rank test and restricted mean survival time (adjusted for county). Restricted mean survival time provides estimates of the mean time to event regardless of event rate whereas conventional median survival time is only computable when the event rate is 50% or greater. Moreover, restricted mean survival time is a more direct and interpretable measure of actual survival time, compared to a hazard ratio derived from a Cox model.
- 8.6. Added county and eliminated Hispanic ethnicity as potential moderators. County (8 unique counties in WA State) was added as a potential moderator, given possible variation by county in GI provider waittimes and other factors. We also eliminated Hispanic ethnicity as a moderator as it has a strong correlation with preferred language.

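### The primary model adjusts for county only and leaves out the colonoscopy-probability score already planned at baseline; adding it is an optional, modest precision gain, assumed to be worth about 1% to 11% more patients.

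*SAP*

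**What the plan says.** - **Covariates.** SAP 5.2: "We will treat county as a covariate in all analyses as it was a randomization stratification variable". No other covariate is listed.
- **Primary model.** SAP 6.1 specifies a logistic model with arm and county as fixed effects: "The model will include county as a covariate (fixed effect) as it was a stratification factor for randomization". Clinic "will be modeled as a random effect", unless the ICC is below .001.
- **The score.** SAP 3: "CHR analysts will assign a colonoscopy completion probability, based on the risk prediction model". SAP 8.1 repeats the commitment after eligibility was widened: "We will still prospectively calculate the patients' estimated probability of obtaining a colonoscopy, using the risk prediction model".
- **Its only analytic use.** SAP 6.3, on moderators: "we will add probability strata (moderate, low vs. high) and the product of stratum and arm to the primary outcome model". Then: "We will repeat this analysis using the continuous risk score in place of the risk strata".
- **Time to colonoscopy.** SAP 8.5 reports restricted mean survival time (RMST) adjusted for county.

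**The concern.** The score predicts the primary outcome itself, and SAP 6.3 describes receipt as varying substantially across its strata. It is therefore the natural baseline adjustment variable, and it costs nothing to collect because it is already planned. In the 6.3 models it always appears with an arm-by-score product. The arm coefficient there is the effect at a reference level of the score, not the overall effect of navigation. As written, no planned analysis reports the overall effect adjusted for the score.

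What is at stake is efficiency. Adjusting for a predictive baseline score raises the power of the arm test, tightens a standardised risk difference and allows for chance imbalance between arms on that predictor.

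**Working it through.** **Inputs from the documents**
- 600 patients per arm, 1:1 (SAP 3).
- 44% completion under usual care; 53.2% (OR 1.45) detectable without a design effect; two-sided alpha .05; ICC .03 (SAP 4).
- Preliminary stratum rates of 30%, 59% and 93% (SAP 6.3). For the highest quintile, 65% in place of the estimated 93% (SAP 8.1).
- Score bands: low below .52, moderate .52 to .63, high .63 and above (SAP 5.3).

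The documents give no R2, c-statistic or stratum shares. Every share below is an assumption, and so are any stratum rates not listed above.

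**The plan's own figures**

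OR = (0.532/0.468) / (0.44/0.56) = 1.45, as stated. A pooled two-proportion calculation with 600 per arm gives power 0.891, not 0.80; 80% power needs 463 per arm. The SAP figure is conservative. That is a separate matter, but it makes 0.89 the baseline here.

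**Size of the gain**

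R2 = (between-stratum variance of p) / [pbar(1 - pbar)], and the patient-equivalent factor is 1/(1 - R2).

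Anchor: suppose 44% overall and 65% in the top fifth describe the same patients and the score is roughly calibrated. The other four fifths then average (0.44 - 0.2 × 0.65)/0.8 = 38.75%. R2 is smallest if they all sit there:

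R2 = (0.2 × 0.21² + 0.8 × 0.0525²)/0.2464 = 0.011025/0.2464 = 0.0447; factor 1.047; 56 of 1200 patients.

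A higher overall rate lowers this minimum. At 54% overall the rest sit at 51.25%, and R2 = (0.2 × 0.11² + 0.8 × 0.0275²)/0.2484 = 0.0122.

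| Assumed rates (shares) | Overall | R2 | Gain in patients | Closed-form power |
|---|---|---|---|---|
| 51.25/65% (80/20) | 54% | 1.2% | +1.2% (15) | 0.895 |
| 46.25/65% (80/20) | 50% | 2.3% | +2.3% (28) | 0.898 |
| A: 45/57/65% (40/40/20) | 53.8% | 2.4% | +2.5% (30) | 0.899 |
| B: 38.75/65% (80/20) | 44% | 4.5% | +4.7% (56) | 0.905 |
| D: 32.5/57.5/65% (60/20/20) | 44% | 8.3% | +9.0% (108) | 0.915 |
| C: 30/59/65% (56/24/20) | 44% | 10.2% | +11.4% (137) | 0.921 |

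Power is for 44% vs 53.2% with 600 per arm multiplied by 1/(1 - R2). In D, 57.5% is the midpoint of the moderate band. C keeps the preliminary 30% and 59% beside the updated 65%.

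**Check in the planned model**

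This was simulated with 6000 runs per setting: 1200 patients, 32 clinics in 8 counties, 1:1 allocation within county, and ICC .03 on the latent scale with the clinic variance held at its true value when fitting. County effects had SD 0.3 on the logit scale (assumed) and were independent of the score. The marginal OR was 1.45. The model with county alone was compared with county plus the logit of the score.

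| Scenario | Variance gain, standardised risk difference | Power | SE of log-OR |
|---|---|---|---|
| A | 2.2% | 0.889 to 0.898 | 0.1207 to 0.1224 |
| B | 4.5% | 0.895 to 0.906 | 0.1190 to 0.1219 |
| D | 8.6% | 0.894 to 0.916 | 0.1189 to 0.1245 |
| C | 11.2% | 0.895 to 0.927 | 0.1188 to 0.1259 |

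The standard error rises, but the conditional OR moves further from 1: 1.471 to 1.486 in A and 1.470 to 1.538 in C. In C the ratio of log-OR to SE goes from 0.385/0.1188 = 3.24 to 0.430/0.1259 = 3.42, and (3.42/3.24)² is about 1.11, which agrees with the variance gain. A permuted, useless score left the variance ratio at 0.998 to 1.001 and power unchanged.

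**The case against.** **No defect.** Adjusting for the stratification factor is a standard, sufficient choice, and power already exceeds 80% at the stated difference. This stands, and it is why the point is optional. A reader might infer that leaving out a strong predictor biases the comparison. It does not, because allocation is randomised.

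**Probably too late.** SAP 8.5 and 8.7 describe RMST, log-rank and sensitivity analyses in the past tense. The evaluation interval ended in December 2022, and reference 2 is dated September 2023. This largely stands. Tense is not proof, but it points to outcomes having been compared by arm. In that case the primary result gains nothing and only a supportive analysis is open.

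**The size is assumed.** This also stands. The upper end mixes two preliminary rates with one updated rate, and overlap of the score with county or clinic would reduce the gain. A reader might put 30/59/93% into the formula and get R2 of 22% to 28%, or 28% to 39% more patients. SAP 8.1 replaced the 93% with 65%, so the documents do not support that.

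**Already available from 6.3.** A standardised overall effect could be derived from the planned interaction model. That is true, but the SAP does not plan to report it.

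**Other stronger readings.** A reader might expect a narrower confidence interval for the odds ratio; the simulation shows the opposite. A reader might carry the gain over to RMST, but every calculation here concerns the binary outcome. A reader might also combine the gain with a full cluster design effect. Patients are randomised individually, and the simulation at ICC .03 shows almost no loss from clustering, so that combination is not supported.

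**Conclusion.** The point holds as an optional improvement. The planned county-only analysis is valid and unbiased, and it forgoes a modest gain of about 1% to 11% more effective patients. About 5% is the best-anchored figure; it requires that the 44% and 65% rates describe the same patients, that the score is roughly calibrated and that the other four fifths are flat. Simulated power rises by 0.9 to 3.2 percentage points, from about 0.89 to 0.90-0.93, and by less at the lowest R2 considered. The benefit lies in the arm test and the standardised risk difference, not in the standard error of the odds ratio. Confidence in the size is medium, because it rests on assumed stratum shares and on a score independent of county and clinic.

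**What to change.** 1. **If outcomes have not been examined by arm:** add the logit of the predicted probability as a fixed effect beside county in the primary model of SAP 6.1, and amend 5.2 to match.
2. **If they have, as the text suggests:** keep the county-only model as primary and report the score-adjusted model as a labelled supportive analysis.
3. **In either case:**
   - Name the score version and confirm that it was built without trial outcomes. Reference 2 describes a recalibrated and redeveloped model, and the SAP does not say which data were used.
   - State a simple rule for missing scores, for example the overall mean plus a missing indicator.
   - Report the standardised risk difference, with a confidence interval that allows for clinic (for example, the delta method from the mixed model), beside the conditional OR. SAP 4 plans on both scales.
4. Adjusting RMST for the score is optional; no gain has been quantified.

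**Cost:** a short SAP paragraph, no new data and one extra standardisation step. The conditional OR will differ slightly from the county-only OR (about 1.47 becomes 1.49 in A and 1.54 in C) and so from the planning OR of 1.45, which the report should explain.
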